**Table 5: Imputation for Prior/Concomitant Medication Missing and Partial Dates**

Parameter	Missing	Additional Conditions	Imputation
Start date for con meds	D only	M and Y are not missing or imputed.	Use 1 st day of M.
	M only	D and Y are not missing or imputed.	M = January
	M and D	Y is not missing or imputed.	Use Jan 01 of Y
	M, D, and Y	None - date completely missing	No imputation but considered concomitant unless stop date is prior to first dose of IP.
Stop date for con meds	D only	M and Y are not missing or imputed.	Last day of month
	M only	D and Y are not missing or imputed.	M = December
	M and D	Y is not missing or imputed	Use Dec 31 of Y
	M, D, and Y	None - date completely missing and NOT ongoing	No imputation

Note: In all cases, if an estimated start date is after a complete stop date, the start date will be set to the end date of medication.

## 5. BASELINE, DISPOSITION, AND EXPOSURE

### 5.1. Study Day and Analysis Window

For all assessments performed on or after the first day of treatment, i.e. reference date  $\geq$  date of first dose of IP, Study Day is calculated as:

- Study Day = (date of assessments/events - first day of treatment) + 1

For assessments performed prior to the first day of treatment, i.e. reference date  $<$  date of first dose of IP, Study Day is calculated as:

- Study Day = date of assessment/event – first day of treatment.

### 5.2. Analysis Visit Windows

#### Efficacy Analyses

Efficacy analyses will use data only from scheduled visits. Data will be reported by designated visit. Data collected at unscheduled visits will be provided in listings. For analysis of data collected across specific study periods, the following definitions will be applied:

- Baseline for efficacy assessments is defined as based on the participant's prior study as follows:
  - Study 1042-TSC-2001 – the original 4-week screening period for participants continuing in Study 1042 TSC-3002
  - Study 1042-TSC-3001 – the original 4-week screening period for participants previously randomized to GNX.
- 3-year open-label treatment period: Visit 2 to Visit 13. All windows for these visits are  $\pm$  14 days.

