### **9.2.6 Subgroup Analysis**

The following subgroup summarizations of the efficacy parameter are planned as outlined in the SAP:

- Gender (Female vs Male).
- Age groups (1 to 6 years; 7 to 12 years; 13 to 17 years; and 18 years and above).

All the analyses will follow the rules:

- The results will be presented overall, for participants previously enrolled in Study 1042-TSC-2001, and for participants previously enrolled in Study 1042-TSC-3001 results will also be classified according to the double-blind treatment received by participants in Study 1042-TSC-3001.
- The seizure endpoints will be derived starting from the first dosing day of OLE treatment.
- No per protocol analyses will be performed

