### **2.3.2. Secondary Endpoints**

The secondary endpoints are:

- Percentage change from baseline in 28-day seizure frequency during open-label treatment (first year only)
- Number (%) of participants considered treatment responders (first year only)
- CGI-I at the last scheduled study visit
- Change from baseline in the quality-of-life scale SF-36 (first year only)
- Change from baseline in the percentage of seizure-free days during treatment, based on seizure type (first year only)
- Change from baseline of CGI-CSID

Note that original baseline in 28-day seizure frequency in the parent study will be applied. For other assessments, the baseline is considered to be Visit 1, the first visit of the OLE.

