## 4.4. Statistical Methods for Secondary Efficacy Analyses

### 4.4.1. Percentage change from baseline in 28-day seizure frequency during open-label treatment.

Seizure types are defined as the following: focal motor seizures without impairment of consciousness or awareness, focal seizures with impairment of consciousness or awareness with motor features, focal seizures evolving to bilateral, tonic-clonic convulsive seizures, and generalized motor seizures including tonic-clonic, bilateral tonic, bilateral clonic, or atonic/drop seizures. Seizures must have a motor component sufficiently prominent and distinct to clearly establish the observed symptoms as epileptic in origin. Seizures that do not count towards the efficacy endpoints include: focal aware seizures without motor features (eg, absence or focal nonmotor seizures with or without impairment of awareness), infantile or epileptic spasms, and myoclonic seizures.

Baseline for efficacy assessments is defined as based on the participant's prior study as follows:

- Study 1042-TSC-2001 – the original 4-week screening period for participants continuing in Study 1042 TSC-3002
- Study 1042-TSC-3001 – the original 4-week screening period for participants previously randomized to GNX.

Post-baseline 28-day seizure frequency will be calculated as the total number of seizures in the open-label phase divided by the number of days with seizure data in the same period, multiplied by 28. Baseline 28-day seizure frequency will be calculated as the total number of seizures in the baseline phase divided by the number of days with seizure data in the same period, multiplied by 28. The calculation for percent change from baseline in 28-day seizure frequency will be done as follows for each participant:

$$\left( \frac{[(\text{Post-baseline 28-day seizure frequency}) - (\text{Baseline 28-day seizure frequency})]}{(\text{Baseline 28-day seizure frequency})} \right) \times 100\%$$

The baseline, post-baseline, and arithmetic and percent changes from baseline in 28-day seizure frequency will be summarized using descriptive statistics. The following subgroup summarizations will be also applied:

- Gender (Female vs Male).
- Age groups (1 to 6 years; 7 to 12 years; 13 to 17 years; and 18 years and above).

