#### **4.4.5. Change from baseline in the percentage of seizure-free days during treatment, based on seizure type**

The percentages of seizure-free days will be based on the primary seizure types. Post-baseline percentage of seizure-free days will be calculated as the number of days in the open-label treatment phase with zero seizures divided by the number of days with seizure data in the phase, multiplied by 100. The baseline percentage of seizure-free days will be calculated as the number of days in the 4-week baseline phase with zero seizures divided by the number of days with seizure data in the baseline phase, multiplied by 100.

The baseline and post-baseline values and the arithmetic changes from baseline will be summarized using descriptive statistics.

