#### **4.5. Handling of Missing Data**

Available data from patients who withdraw from the study prematurely will be included in analyses, unless otherwise indicated. Summary statistics will be reported based upon observed data. No data will be imputed or carried forward for missing values or for patients who discontinue early. All missing data and missing or partial dates for AEs and medications will be queried for a value. In the unlikely event that no value can be obtained, substitutions will be made as described below.

- Missing and Partial Start/Stop Dates - AEs and Concomitant Medications**

The handling of partial start and stop dates for AEs are described in

**Table 4** below. Similar algorithms for handling missing and partial dates of concomitant medication usage are described in **Table 5**. In both cases, if a stop date is complete and an imputed start date is after the stop date, the start date will be set to the stop date.

- **Missing Seizure/Medication Diary Entries**

The calculation of seizure frequency endpoints will include only days for which diary entries are available. Missing seizure data will not be imputed.

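### SAP 5.2 starts the efficacy open-label period at Visit 2, against the protocol's first-dose start and the first-year limit, and the 3001 baseline bullets omit former-placebo participants

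*SAP*

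**What the plan says.** **Period.** SAP 5.2 introduces its efficacy bullets with "For analysis of data collected across specific study periods, the following definitions will be applied". The baseline comes first, then "3-year open-label treatment period: Visit 2 to Visit 13", followed by a ±14-day window for those visits. The Schedule of Activities (Protocol 1.3) counts weeks from the first OLE dose. It places Visit 2, a phone contact, at Week 13, Visit 5 at Week 52 and Visit 13 at Week 156.

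Protocol 9.2.6, among its rules for all analyses, states: "The seizure endpoints will be derived starting from the first dosing day of OLE treatment". SAP 2.3.2 lists "Percentage change from baseline in 28-day seizure frequency during open-label treatment (first year only") and puts the same limit on responders and seizure-free days. Daily diary entries are planned for the first year only (Protocol 4.1).

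The derivations refer to the open-label phase without dating it. SAP 4.4.1 uses "the total number of seizures in the open-label phase divided by the number of days with seizure data in the same period", multiplied by 28. SAP 4.4.5 uses "the number of days in the open-label treatment phase with zero seizures" as its numerator.

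**Baseline.** For Study 3001, the efficacy-baseline bullets in SAP 4.4.1 and 5.2, and footnote a to the objectives table in Protocol 1.1 and 3, cover only participants previously randomised to GNX. The note in SAP 2.3.2 applies the parent-study baseline for 28-day frequency with no restriction by arm. SAP 4.4.5 likewise uses a 4-week baseline phase without restriction.

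**The concern.** One period feeds four outputs: percent change in 28-day frequency, responder status, the cumulative responder curve and seizure-free days. The only dated open-label period in the SAP does not match the protocol's rule for those outputs, so two programmers could derive different values from the same diary.

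The early weeks also bear on who is counted. SAP 4.5 says: "Available data from patients who withdraw from the study prematurely will be included in analyses, unless otherwise indicated". Under a Visit 2 start, someone who leaves before Week 13 contributes no post-baseline diary days. That person drops out of the percent-change summary, which then describes only those who stayed.

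The baseline gap raises a second question. Former-placebo participants were titrated to GNX before the parent study ended (Protocol 1.1, SAP 1), so OLE Visit 1 is not a pre-GNX baseline for them. They belong to the efficacy set (Protocol 9.1, SAP 4.2), and SAP 4.4.2 shows treatment groups separately on the responder curve. The detailed rule says nothing about their baseline.

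**Working it through.** The study is descriptive and unpowered, so there is no sample-size figure to reproduce. The check is calendar arithmetic on the Schedule of Activities, plus a comparison of the baseline statements.

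**1. Does the label fit the period?** Visit 2 to Visit 13 is 156 − 13 = 143 weeks, and 143/52 = 2.75 years, not 3.

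**2. Year 1 diary days before Visit 2**
- Year 1: 52 × 7 = 364 days.
- Nominal Visit 2: 13 × 7 = 91 days; 91/364 = 25.0%. This leaves 273 days.
- Visit 2 two weeks early (Week 11): 77/364 = 21.2%.
- Visit 2 two weeks late (Week 15): 105/364 = 28.8%.
- If Visit 5 also moves within its window (Week 50 to 54): from 77/378 = 20.4% to 105/350 = 30.0%.
- Participant stopping before Visit 2: 100% of diary days fall outside the period.

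**3. The end of the period.** Of the 143 weeks, 52 − 13 = 39 (27.3%) lie in the diary year and 104 (72.7%) lie after it. This has little numerical effect, because diaries stop after Year 1 and SAP 4.5 states: "The calculation of seizure frequency endpoints will include only days for which diary entries are available". Entries late in the Visit 5 window, or during taper after an early stop (Protocol 8.1.2 asks for the diary then), are the residual cases.

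**4. Can the start date change a result?** The documents give no OLE seizure rates, so the rates below are assumed for illustration only. Baseline is 20 per 28 days.

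| Weeks 0–13 | Weeks 13–52 | Rate from first dose | Change from first dose | Change from Visit 2 |
|---|---|---|---|---|
| 16 | 9 | (16×13 + 9×39)/52 = 10.75 | (10.75 − 20)/20 = −46.25% | (9 − 20)/20 = −55.0% |
| 10 | 10 | 10 | −50.0% | −50.0% |
| 9 | 12 | (9×13 + 12×39)/52 = 11.25 | (11.25 − 20)/20 = −43.75% | (12 − 20)/20 = −40.0% |

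In the first row the participant is a non-responder from first dose and a responder from Visit 2. In the third row the shift goes the other way, so no direction of bias can be claimed.

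**5. Baseline statements side by side**

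| Place | Former-placebo participants from 3001 |
|---|---|
| SAP 4.4.1 and 5.2 bullets; Protocol 1.1 and 3, footnote a | Not covered; GNX-randomised only |
| SAP 2.3.2 note | Covered for 28-day frequency, and so by extension for responders; Visit 1 for other assessments |
| SAP 4.4.5 | 4-week baseline phase, no restriction |
| Protocol 9.1; SAP 4.2 and 4.4.2 | In the efficacy set; shown by arm |

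The general statements point to the parent-study baseline for everyone, while the detailed ones stop short of it. The number of participants affected cannot be given, because the documents do not state the 3001 allocation or rollover by arm.

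**The case against.** The best counter-argument is that the SAP line is a visit list. It sits under a visit-window heading in a section that limits efficacy analyses to scheduled visits. Its ±14-day sentence repeats the schedule header, which covers Visits 2 to 13 and excludes Visit 1. The 3-year label fits Week 0 to Week 156, which itself counts against the literal reading. Clinician and caregiver global ratings run to Visit 13, so a 3-year efficacy span has a use. Protocol 8.1.2 dates the open-label phase from the first OLE dose, SAP 5.1 makes that day Study Day 1, and SAP 6 declares no departure from the protocol's analyses. On this view the correct start can be recovered and only a cross-reference is missing. The programming specifications and shells, which are separate documents, may settle it.

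Much of this is fair. The visit-list reading is plausible, and under it no diary day is lost. But Protocol 8.1.2 and SAP 5.1 fix a time origin; they do not define an analysis period. The SAP introduces the line as a definition for data collected across periods, and the bullet beside it is a 4-week diary interval rather than a visit. The first-dosing-day rule is not repeated in the SAP, and the shells are not available to judge.

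It can also be said that, for a participant who stops before Visit 2, the period is undefined rather than empty. Either way no usable rule covers that person's diary days.

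On baseline, the SAP 2.3.2 note and SAP 4.4.5 do supply most of the answer. What remains is a detailed rule that contradicts them by omission.

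**Conclusion.** The concern holds. Followed as written, SAP 5.2 contradicts the protocol's start for the seizure endpoints, the SAP's own first-year limit and its own 3-year label. The start date is the material part: 25% of Year 1 diary days fall outside the period (21% to 29% across the Visit 2 window), and all of them for anyone who stops before Visit 2. These figures apply only to the literal reading and assume the nominal schedule. The Week 156 end matters little. The effect on estimates is unknown in size and direction.

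The 3001 baseline bullets are separately incomplete for an arm that the plan analyses and displays.

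Importance is minor to moderate. The endpoints are secondary and descriptive, with no error rate or power at stake, and the primary safety results are untouched. It should still be fixed, because the stated rules give contradictory derivations and the correction is small.

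**What to change.** 1. In SAP 5.2, define a seizure-diary period from the first OLE dose (Day 1) through Week 52 (Visit 5), or the last diary day if earlier. Use that term in SAP 4.4.1, 4.4.2 and 4.4.5.
2. If Visit 2 to Visit 13 is kept, label it as the list of scheduled post-baseline visits; it suits the two global-impression scales, which continue to Visit 13.
3. In SAP 4.4.1 and 5.2, remove the GNX-only qualifier so that the original 4-week parent-study baseline applies to every 3001 participant, for seizure-free days as well as 28-day frequency.
4. Align footnote a in Protocol 1.1 and 3 with this.

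The cost is wording in four SAP sections, which SAP 6 allows by amendment before database lock. The protocol footnote can wait for a later amendment, since any amendment needs ethics approval (Protocol 10.1.1) and the SAP is the detailed source for the analyses. No new data are required: OLE diaries already cover the first year, and the baseline diaries come from the parent studies.

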#### Safety Analyses

Safety data will be summarized by actual visit. No visit windowing will be applied.

### 5.3. Demographics

Demographics will be summarized and listed for all patients in the Safety Population. Demographic characteristics, including age, height, weight, and BMI, will be summarized with descriptive statistics (n, mean, median, SD, minimum and maximum). Categorical characteristics such as age group ( $\leq$  17 years,  $>$  17 years), weight group ( $\leq$  28 kg,  $>$  28 kg), sex, race and ethnicity, will be summarized as counts and percentages.

## **5.4. Subject Disposition**

The number of patients screened for this study, the number of rollover (from TSC-2001 and 3001) and the number of patients who received at least one dose of IP will be summarized. The final disposition of all patients who receive IP will be summarized. Reasons for discontinuation of study participation will be summarized. The total number and percentage of patients who complete the study will be summarized.

A listing of patient disposition will be provided. In addition, a summary of the number of patients included in each analysis set will be presented.

## **5.5. Prior and Concomitant Medications**

All investigator terms for medications recorded on the CRF will be coded using the World Health Organization Drug Dictionary Enhanced (WHODDE) Anatomical Therapeutic Chemical (ATC) drug dictionary. The number (percentage) of subjects who took prior and concomitant medications will be summarized in the Safety population by Anatomic Therapeutic Chemical (ATC) classification level 2 and Preferred Term (PT).

Prior medications are defined as medications that started prior to the first dose of study drug. Concomitant medications are defined as medications (other than the study drug) taken on or after the first dose of the study drug. Medications started before the first dose of study drug and continuing at the time of the first dose of study drug are considered both prior medication and concomitant medication.

The number and percentage of patients in the Safety population reporting use of prior and concomitant treatments will be summarized and listed separately. In addition, anti - seizure medication (ASM) and rescue medications will be presented separately.

## **5.6. Medical History**

Medical history will be coded using Medical Dictionary for Regulatory Activities (MedDRA), version 23.0. The number and percent of subjects with clinically significant medical history at screening will be summarized by system organ class (SOC) and preferred term (PT) in the Safety population. Medical history will also be listed.

## **5.7. Study Drug Exposure**

Exposure to study medication (GNX) will be summarized as the number of days on treatment, percentage of days dosed, maximum daily dose received, and total dosage received. The denominator for the percentage of days of study drug is the number of days the patient is on treatment in the respective part of the study. If the patient stops taking IP during the study, the last day that drug was taken will be used as the last day of treatment. For patients who are ongoing at the end of a specific part of the study, the last known treatment date will be used for the last day on treatment.

A listing of exposure data for each patient including total daily dose, start and end dates, and reason for any dose change will also be provided.

### **5.8. Study Drug Compliance**

Compliance with GNX treatment will be assessed by inspecting the seizure and medication diary entries and returned drug supply with queries as necessary. The percent compliance with study drug will be estimated using dosing information reported in the eDiary as follows:

$$\frac{[\text{number of days with study medication taken} = \text{Yes}]}{(\text{number of days with study medication taken reported})} \times 100$$

Reported dosing by visit and calculated compliance values will be listed.

## **6 SUMMARY OF MAJOR CHANGES IN THE PLANNED ANALYSES**

No other changes are made to the protocol specified analyses.

Any further analysis changes made after this SAP is finalized, but prior to database lock, will be documented with an SAP amendment. If after database lock, analysis changes or additional analyses required to supplement the planned analyses within this SAP will be described in the clinical study report (CSR).

## **7 PROGRAMMING SPECIFICATIONS**

Programming specifications will be provided in the SAP table, listing, and figures shells document.

## **8 TABLES, LISTINGS, AND FIGURES SHELLS**

The tables, listing, and figures shells will be provided as a separate document.
